## 6 STUDY POPULATION

For entry into the study, the following criteria MUST be met.

### 6.1 Inclusion Criteria

#### 1) Signed Written Informed Consent

- a) Participants must have signed and dated an IRB/IEC approved written informed consent form in accordance with regulatory and institutional guidelines. This must be obtained before the performance of any protocol related procedures that are not part of normal participant care.

- b) Participants must be willing and able to comply with scheduled visits, treatment schedule, laboratory tests, tumor biopsies, and other requirements of the study.

## 2) Type of Participant and Target Disease Characteristics

- a) Participants must be at least 18 years old and have histological or cytological confirmation of metastatic and/or unresectable metastatic colorectal, pancreatic, breast, ovarian, or urothelial carcinoma with measurable disease per RECIST v1.1 or per PCWG3 criteria for prostate carcinoma (see [Appendix 7](#) or [Appendix 8](#), respectively).
- b) Presence of at least 2 lesions: at least one with measurable disease as defined by RECIST v1.1 (per PCWG3 criteria for prostate carcinoma) for solid tumors for response assessment; at least 1 lesion must be accessible for biopsy in addition to the target lesion.
- c) Participants with lesions in a previously irradiated field as the sole site of measurable disease will be permitted to enroll provided the lesion(s) have demonstrated clear progression and can be measured.
- d) Participants must have received, and then progressed or been intolerant to, at least 1 standard treatment regimen in the advanced or metastatic setting, if such a therapy exists, and have been considered for all other potentially efficacious therapies prior to enrollment. Participants who are ineligible for standard therapy (due to medical factors such as comorbid illness, age, etc.) will be allowed to enroll provided the reason for their ineligibility is documented in their medical records. Specific details are provided in [Section 3](#)) below for each indication.
- e) The Dose Escalation (Parts 1 and 2)
  - i) Participants with colorectal, prostate, urothelial, ovarian, triple-negative breast, or pancreatic carcinoma will be permitted.
  - ii) All comers CD8 TIL are permitted in Parts 1 and 2. However, at least 3 participants with low or mid CD8 TIL must be evaluated at each dose level in Part 2.
- f) The Expansion (Part 3)
  - i) Participants must have tumors classified by CD8+ TILs prior to treatment to determine cohort assignment:
    - (1) Low:  $CD8 < 2\%$
    - (2) Mid:  $2\% \leq CD8 < 20\%$
    - (3) High:  $\geq 20\%$
- g) ECOG performance status  $\leq 2$ .
- h) Prior palliative radiotherapy must have been completed at least 2 weeks prior to the first dose of the study treatment. Participants with symptomatic tumor lesions at baseline that may require palliative radiotherapy within 4 weeks of the first dose of study treatment are strongly encouraged to receive palliative radiotherapy prior to enrollment.
- i) Participants with prior exposure to therapy with any agent specifically targeting checkpoint pathway inhibition (such as anti-PD-1, anti-PD-L1, or anti-CTLA-4) are permitted after a washout period of any time greater than 4 weeks from the last treatment.

### 3) The Following Tumor Types Will Be Explored:

- a) **Colorectal Cancer (CRC):** Participants with histologically confirmed CRC that is metastatic or recurrent with documented disease progression and that meets all of the following:
  - i) Document microsatellite instability, mismatch repair, KRAS, and BRAF status, if known.
  - ii) Prior therapy requirement: Participants must have received at least 1, but no more than 3, prior systemic therapies for metastatic and/or unresectable disease (or have progressed within 6 months of adjuvant therapy).
  - iii) Participant must have incurable metastatic disease (ie, participants with disease that is potentially curable by surgical resection are not eligible for treatment).
  - iv) **Prior therapy requirement as of Revised Protocol 05:** Participants must have been offered an oxaliplatin-containing regimen and an irinotecan-containing regimen (including as part of a combined oxaliplatin- and irinotecan-containing regimen). If the participant refuses these regimens, the reason must be documented in the medical record.
- b) **Prostate Cancer:** Participants with histologically or cytologically confirmed adenocarcinoma of the prostate and that meet all of the following:
  - i) Metastatic disease by any 1 of the following modalities: computerized tomography (CT), magnetic resonance imaging (MRI), and/or bone scan.
  - ii) Participants with bone-only disease should have progression confirmed as per PCWG3 criteria and require confirmatory scans.
  - iii) Prior therapy, participants:
    - (1) Must have been treated by orchiectomy or are receiving a luteinizing hormone-releasing hormone analog, and have a testosterone level  $\leq 50$  ng/dL.
    - (2) Must have received abiraterone or enzalutamide.
    - (3) May have received anti-androgens (bicalutamide, flutamide, nilutamide) or adrenal androgen production inhibitors (aminoglutethamide or ketoconazole) therapy. This therapy should be discontinued prior to starting study treatment:
      - (a) Participants with a history of response to an anti-androgen or adrenal androgen production inhibitor and subsequent progression should be assessed for anti-androgen withdrawal response for 4 weeks, and must demonstrate progression as described in inclusion criteria below (iv)
      - (b) For participants who have never responded to anti-androgens, observation for anti-androgen withdrawal response is not necessary; however, a 2-week washout period is required prior to start of study treatment
    - (4) No more than 1 chemotherapeutic regiment for mCRPC.
  - iv) Participants treated with hormonal therapy must have progressed during treatment. For eligibility purposes, PD is defined as:
    - (1) Rising prostate-specific antigen values at a minimum of 1-week intervals and a 2.0-ng/mL minimum starting valueOR

- (2) Progression per bone scan: the appearance of 2 or more new lesions  
OR
  - (3) Progression per target lesions/measurable disease: nodal progression, per modified RECIST v1.1. Only lymph nodes > 2 cm will be considered to assess a change in size qualifying for disease progression.
- c) **Urothelial Cancer:** Participants with histologically confirmed urothelial carcinoma (originating in bladder, ureter, or renal pelvis) who meet all of the following criteria:
- i) Histological or cytological evidence of metastatic or surgically unresectable transitional cell carcinoma of the urothelium involving the bladder, urethra, ureter, or renal pelvis. Minor histologic variants (< 50% overall) are acceptable.
  - ii) Participants must have metastatic or surgically unresectable (cT4b, or any N+ [N1-3], or any M-1) disease.
  - iii) Participants must have progression or recurrence after treatment:
    - (1) With at least 1 platinum-containing chemotherapy regimen (if platinum eligible) but no more than 2 regimens for metastatic or surgically unresectable locally advanced urothelial cancer  
OR
    - (2) Within 12 months of peri-operative (neo-adjuvant or adjuvant) treatment with a platinum agent in the setting of cystectomy for localized muscle-invasive urothelial cancer.
  - iv) Participants may have received prior Bacillus Calmette–Guérin (BCG) vaccine and/or anti-PD-1/PD-L1 therapies.
  - v) Sequential chemotherapy given as a planned sequence to optimize response will count as 1 regimen.
- d) **Ovarian Cancer:** Participants with histologically confirmed ovarian carcinoma (including epithelial ovarian cancer, primary peritoneal, fallopian tube carcinoma, or clear cell carcinoma) who must meet all of the following:
- i) Documented somatic or germline BRCA status, if known. If unknown, participants must consent to allow the fresh tumor tissue to be tested. Participants can also submit an additional archived tumor tissue sample (block or unstained slides) to be tested. The archived tumor tissue sample is not a substitute for the fresh tumor tissue sample.
  - ii) Participants must have received no more than 5 prior systemic lines of therapy.
    - (1) A line of therapy is defined as a regimen used to treat initial disease (frontline) or following disease progression (second and subsequent lines). A change in regimen for reasons of toxicity or consolidation/maintenance in the absence of disease progression does not constitute a new line of therapy.
    - (2) One regimen must have been a prior platinum-based chemotherapeutic regimen for management of primary disease, possibly including intraperitoneal therapy,

- consolidation, biologic/targeted (non-cytotoxic) agents (eg, bevacizumab) or extended therapy administered after surgical or non-surgical assessment.
- (3) For the purposes of this study, PARP inhibitors given for recurrent or progressive disease will be considered a line of therapy. PARP inhibitors given as maintenance therapy will not be considered another line of therapy.
- (4) **As of Revised Protocol 05**, participants with refractory ascites, indwelling gastric drainage catheters for bowel obstruction, or bowel obstruction within 1 month of consent are excluded.
- (5) **As of Revised Protocol 05**, participants who have undergone diverting colostomy/ileostomy for bowel obstruction will be eligible, provided that they have been free of obstructive symptoms for > 1 month.
- iii) Participants must have progressed less than 12 months after completion of their last platinum-based therapy. The number of months (platinum-free interval) should be calculated from the date of the last administered dose of platinum therapy to the date of the documented progression.
- iv) **As of Revised Protocol 05**, participants with histologic subtypes of carcinosarcoma, mucinous, and low grade serous cancers are excluded.
- e) **Triple-Negative Breast Cancer (TNBC)**: Women with histologically or cytologically confirmed breast carcinoma who must meet all of the following:
- i) Tumor must be “triple receptor negative” defined as ER/progesterone negative per local lab and HER-2 negative defined as HER-2 0 or 1+ by IHC, or IHC 2+ and ISH not amplified, or ISH-non amplified.

AND

- ii) Participants must have progression or refractory disease. Participants must have had at least 1 and not more than 2 chemotherapeutic regimens for the treatment of metastatic or locally advanced and unresectable disease

OR

- iii) Participants may refuse chemotherapy for their disease. Participants actively refusing chemotherapy must have had best response of stable disease, or progression or refractory disease to other treatment options such as radiotherapy, targeted agents, or investigational therapy prior to starting study treatment. The participant’s refusal must be thoroughly documented. The investigator will discuss each individual participant refusing chemotherapy with the sponsor’s Medical Monitor (or designee) to confirm eligibility.
- f) **Pancreatic Cancer**: Participants with histologically confirmed pancreatic adenocarcinoma who meet all of the following:
- i) Participants must not have clinically relevant ascites at baseline, such as ascites in need of paracentesis

AND

- ii) Participants must have had best response of stable disease, or progression or refractory disease during or after at least 1 but not more than 2 chemotherapeutic regimens for the treatment of metastatic (Stage IV) or locally advanced disease

OR

iii) Participants may refuse chemotherapy for their disease. Participants actively refusing chemotherapy must have had best response of stable disease, or progression or refractory disease to other treatment options such as radiotherapy, targeted agents, or investigational therapy prior to starting study treatment. The participant's refusal must be thoroughly documented. The investigator will discuss each individual participant refusing chemotherapy with the sponsor's Medical Monitor (or designee) to confirm eligibility.

4) **Physical and Laboratory Test Findings**

a) Adequate hematologic function

i) White blood cells  $\geq 2,000/\mu\text{L}$

ii) Neutrophils  $\geq 1,500/\mu\text{L}$  (stable off any growth factor within 4 weeks of first study treatment administration)

iii) Platelets  $\geq 100 \times 10^3/\mu\text{L}$  (transfusion to achieve this level is not permitted within 2 weeks of first study treatment administration)

iv) Hemoglobin  $\geq 9.0$  g/dL (transfusion to achieve this level is not permitted within 2 weeks of first study treatment administration)

b) Adequate hepatic function

i) ALT and AST  $\leq 3 \times$  upper limit of normal (ULN)

ii) Total bilirubin  $\leq 1.5 \times$  ULN (except participants with Gilbert's syndrome who must have normal direct bilirubin)

c) Normal thyroid function or stable on hormone supplementation per investigator assessment

d) Serum creatinine  $\leq 1.5 \times$  ULN or creatinine clearance (CrCl)  $\geq 50$  mL/min (measured using the Cockcroft-Gault formula below):

$$\text{Female CrCl} = \frac{(140 - \text{age in years}) \times \text{weight in kg} \times 0.85}{72 \times \text{serum creatinine in mg/dL}}$$

$$\text{Male CrCl} = \frac{(140 - \text{age in years}) \times \text{weight in kg} \times 1.00}{72 \times \text{serum creatinine in mg/dL}}$$

e) Ability to comply with treatment, PK and pharmacodynamic sample collection, and required study follow-up

f) Participant re-enrollment: This study permits the re-enrollment of a participant who has discontinued the study as a pretreatment failure (eg, participant has not been treated). If re-enrolled, the participant must be re-consented

g) Willing to consent to tumor biopsies during the study

h) All participants must provide a fresh tumor biopsy from the disease site (when possible) or from any metastatic site when the primary site is not available. Collection of the fresh tumor biopsy must be performed at minimal acceptable clinical risk as judged by the investigator. Participants who are unable to provide a fresh tumor biopsy are not eligible for this study. For Parts 2 and 3 of the study, part of the samples will be used prospectively for CD8 evaluation by IHC. All tissue samples must be suitable for testing to verify both CD8 and PD-L1 status by IHC. Refer to the Laboratory Manual and [Section 9.8](#) for further

details on procedures for collecting fresh tumor samples and for determining suitability for both CD8 and PD-L1 IHC

- i) If possible, the immediate confirmation (eg, touch imprint cytopathology) for presence of  $\geq 100$  viable tumor cells from collected tissue samples is strongly recommended by participating sites prior to submitting samples
- j) Prior palliative radiotherapy completed at least 2 weeks before study treatment administration

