### **9.1.3 Secondary Efficacy Assessments**

The secondary efficacy assessments will include the ORR (eg, PR + CR), DCR, mDOR, mPFS and PFSR at 8, 16, and 24 weeks (dependent on indication) based on assessment of tumor response using RECIST v1.1 or PCWG3.

ORR is defined as the proportion of all treated participants whose best overall response (BOR) is either a CR or PR. BOR is defined as the best response designation over the study as a whole, recorded between the dates of first dose until the last tumor assessment prior to subsequent therapy. For participants whose treatment continued beyond RECIST v1.1 or PCWG3 defined disease progression, BOR is defined as the best response recorded between the dates of first dose until the time of the initial disease progression defined by RECIST v1.1 or PCWG3. CR or PR determinations included in the BOR assessment must be confirmed by a second scan performed no less than 4 weeks after the criteria for response are first met. For those participants who have

surgical resection, only pre-surgical tumor assessments will be considered in the determination of BOR.

DCR is defined as the proportion of all treated participants who have achieved CR, PR, and SD. BOR for a participant will be assessed per RECIST v1.1 or PCWG3 by BICR and/or by investigator, where available.

mDOR, computed for all treated participants with a BOR of CR or PR, is defined as the time between the date of first response and the date of disease progression or death, whichever occurs first.

PFS for a participant is defined as the time from the first dosing date to the date of first objectively documented disease progression or death due to any cause, whichever occurs first. mPFS and PFSR will be assessed at 8, 16, and 24 weeks (indication dependent).

The proportion will be calculated by the Kaplan-Meier estimate, which takes into account censored data.

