### 2.3.2 Time Point Response

At each protocol specified time point, a response assessment occurs. Table 2.3.2-1 provides a summary of the overall response status calculation at each time point for patients who have measurable disease at baseline. When patients have non-measurable (therefore non-target) disease only, Table 2.3.2-2 is to be used.

Table 2.3.2-1: Time Point Response: Patients With Target (± Non-Target) Disease			
Target Lesions	Non-Target Lesions	New Lesions	Overall Response
CR	CR	No	CR
CR	Non-CR/non-PD	No	PR
CR	Not evaluated	No	PR
PR	Non-PD or not all evaluated	No	PR
SD	Non-PD or not all evaluated	No	SD
Not all evaluated	Non-PD	No	NE
PD	Any	Yes or No	PD
Any	PD	Yes or No	PD
Any	Any	Yes	PD

CR = complete response, PR = partial response, SD = stable disease, PD = progressive disease and NE = inevaluable

Table 2.3.2-2: Time Point Response: Patients with Non-target Disease Only		
Non-Target Lesions	New Lesions	Overall Response
CR	No	CR
Non-CR/non-PD	No	Non-CR/non-PD a
Not all evaluated	No	NE
Unequivocal PD	Yes or No	PD
Any	Yes	PD
CR = complete response, PD = progressive disease and NE = inevaluable		

a Non-CR/non-PD is preferred over SD for non-target disease since SD is increasingly used as endpoint for assessment of efficacy in some trials so to assign this category when no lesions can be measured is not advised.

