#### **At Entrance:**

In the event that either of the following occur, the study team will consider whether the time relative to first dose is acceptable to be considered as the baseline assessment.

- Participants with a tumor tissue sample earlier than 35 days prior to first dose
- Participants whose baseline efficacy assessments are more than 28 days prior to first dose In the event that any of the following occur, the participants may be excluded from specific (or all) analyses upon study team agreement. Any exclusions due to relevant protocol deviations will be documented in the CSR.
- Participants in Parts 2 and 3 without an evaluable CD8 value prior to first dose.
- Participants without measurable disease at baseline (Inclusion Criteria 2.b).
- Participants in Parts 2 and 3 with a CD8 value  $\geq 20\%$  (Inclusion Criteria 2.f).
- Participants with screening ECOG performance status > 2 (Inclusion Criteria 2.g).
- Participants with prior exposure to checkpoint inhibitors or cytotoxic agents within 28 days prior to first dose (Inclusion Criteria 2.i and Exclusion Criteria 2.a).
- Participants with prior antiviral agents within 7 days prior to first dose or PEG-IFN within 14 days prior to first dose (Exclusion Criteria 2.e).

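### Eligibility requires measurable disease yet sets a condition for bone-only prostate cancer, and no rule says how such a participant would count in DCR or when they may be excluded

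*Protocol*

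**What the plan says.** Protocol Section 6 introduces the criteria with "For entry into the study, the following criteria MUST be met". Criterion 2.b then asks for "Presence of at least 2 lesions: at least one with measurable disease as defined by RECIST v1.1", with PCWG3 as the standard for prostate cancer, and for a further lesion that can be biopsied. Criterion 2.a points to Appendix 8 for the PCWG3 standard. Appendix 8 (sections 1 to 1.3) sorts only soft tissue lesions and lymph nodes into measurable and non-measurable, and follows bone lesions by radionuclide scan.

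The prostate criteria read differently. Criterion 3.b.i accepts "Metastatic disease by any 1 of the following modalities: computerized tomography (CT), magnetic resonance imaging (MRI), and/or bone scan". Criterion 3.b.ii adds "Participants with bone-only disease should have progression confirmed as per PCWG3 criteria", together with a call for confirmatory scans. Neither says that 2.b is waived.

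On scoring, Appendix 8 section 2.3.2 sends participants without measurable disease to Table 2.3.2-2, whose outcomes are CR, Non-CR/non-PD, NE and PD. Its footnote states that "Non-CR/non-PD is preferred over SD for non-target disease". Protocol 9.1.3 states: "DCR is defined as the proportion of all treated participants who have achieved CR, PR, and SD". SAP 8.5 makes All Treated the population for the final efficacy analyses.

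SAP 8.2.3 lists "Participants without measurable disease at baseline (Inclusion Criteria 2.b") among the relevant deviations for which the study team may agree to exclude participants from some or all analyses. Exclusions are to be documented in the CSR.

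**The concern.** A condition written for bone-only disease has no purpose if bone-only disease is already ineligible, so a site could reasonably take 3.b.ii as permission to enrol. Such a participant would then meet three rules that do not fit together:

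- The response table gives no PR and advises against SD.
- DCR counts only CR, PR and SD over all treated, and nothing maps Non-CR/non-PD into it. The best-overall-response table in Appendix 8 (Table 2.3.3-1) has no row for that category either.
- The SAP treats the participant as a deviation whose inclusion is settled case by case, in an open-label trial.

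At stake are who is enrolled, how a stable participant is scored, and whether the ORR and DCR denominators are fixed in advance. The responder counts in Protocol 10.1.2.1 and 10.1.2.2 assume that every participant in the stated N has the assumed chance of response.

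**Working it through.** **Step 1: can a bone-only participant meet 2.b?** Under Appendix 8, measurable means a soft tissue lesion or node of sufficient size, and bone is assessed by scan only. A bone-only participant has no measurable lesion and so fails 2.b. Criteria 3.b.i and 3.b.ii nevertheless describe that participant as a candidate. The conflict is in the text and needs no arithmetic.

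**Step 2: which outcomes are open?** Table 2.3.2-2 is the only table in Appendix 8 for participants without target disease.

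| Outcome | Open to a bone-only participant? | Counts in ORR | Counts in DCR |
|---|---|---|---|
| CR | Yes | Yes | Yes |
| PR | No | Yes | Yes |
| SD | Advised against | No | Yes |
| Non-CR/non-PD | Yes | No | No rule; not listed |
| NE, PD | Yes | No | No |

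Each stable bone-only participant therefore lowers DCR by 1/35 = 2.9 percentage points (Cohort 1) or 1/33 = 3.0 points (Cohort 2) compared with a stable participant who has a target lesion. SAP 8.5 also summarises by indication, and Protocol 7.2 asks for at least 5 participants per selected indication in each cohort. In a prostate group of 5, one such participant moves DCR by 1/5 = 20 points.

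**Step 3: reproduce the plan's power.** The formula is the exact binomial tail P(X ≥ r | N, p).

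- Cohort 1 (N = 35, r = 5, rates 6% and 20%): type I error 0.0563, power 0.8565. The plan states 0.056 and 0.857.
- Cohort 2 (N = 33, r = 11, rates 20% and 40%): type I error 0.0508, power 0.8310. The plan states 0.051 and 0.831.

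The plan's figures are correct.

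**Step 4: illustrate the effect on power.** Assume that k of the N are bone-only and do not respond, with r unchanged. Power is P(X ≥ r | N − k, p1). The value of k is an assumption, because the documents give none.

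| k | Cohort 1: at least 5, p1 = 20% | Cohort 2: at least 11, p1 = 40% |
|---|---|---|
| 0 | 0.857 | 0.831 |
| 1 | 0.838 | 0.795 |
| 2 | 0.818 | 0.755 |
| 3 | 0.796 | 0.709 |
| 4 | 0.771 | 0.657 |
| 5 | 0.745 | 0.601 |

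Power drops below the nominal 0.80 from k = 3 in Cohort 1 and from k = 1 in Cohort 2. The type I error falls as well: at k = 5 it is 0.0315 in Cohort 1 and 0.0149 in Cohort 2.

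**Step 5: what the exclusion option does.** Five responders give 5/35 = 14.3% with everyone counted. If five bone-only participants are excluded, they give 5/30 = 16.7%. The SAP fixes neither denominator for this case.

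**The case against.** The strongest reply is that the consequences arise only if the protocol is broken. The criteria are cumulative, Section 6.2 closes by insisting that all of them be met in full, and Section 9 allows no waivers and requires eligibility to be confirmed before treatment assignment. Section 3.b adds prostate conditions without relaxing 2.b, and SAP 8.2.3 itself treats missing measurable disease as a deviation from 2.b. On that reading no bone-only participant enters and 3.b.ii has no effect. This stands as a limit on the consequences. It does not explain why 3.b.ii is there, and it leaves sites to choose between two criteria.

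Other parts of the reply also stand:

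- The count k has no source. Protocol 5.1.3 lets enrolment focus on two indications per cohort, so prostate cancer may contribute few participants or none.
- CR remains possible for a bone-only participant.
- Protocol 10.1.2 allows up to 40 per cohort. With 5 bone-only participants among 40, 35 others remain, which covers the required 35 and 33.
- Exclusions must be reported in the CSR, and a response-evaluable analysis restricted to measurable disease already exists as supportive.
- Efficacy is a secondary objective.

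A reader might infer three stronger things that the documents do not support. One is that bone-only participants will in fact be in the denominators; that depends on how sites resolve the conflict. Another is that they cannot count as responders at all; only PR is closed to them. The third is that the main PFS and response analyses use different sets; both use All Treated.

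**Conclusion.** The point holds as a contradiction in the eligibility text, with a gap in the scoring and exclusion rules behind it. The contradiction and the missing DCR mapping follow from the documents alone. Any loss of power is conditional on a site enrolling under 3.b, on the assumed k, on no CR among those participants, and on the cohort stopping at 35 or 33. For a given k, the tabulated losses are therefore upper bounds, and the table should not be read as a forecast. The primary objectives, safety and dose selection, are not shown to be affected. The correction is still worth making: it settles who may be enrolled and how they are counted, and Cohort 2 has little margin, since one non-responding bone-only participant within its 33 takes power to 0.795.

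**What to change.** **Protocol.** Reconcile 2.a/2.b with 3.b.i and 3.b.ii in one of two ways. Either state that bone-only disease does not meet 2.b and remove or reword 3.b.ii, or write an explicit exception to 2.b for bone-only prostate cancer. Which population to admit is the sponsor's choice.

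**SAP.**

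- Pre-specify that Non-CR/non-PD meeting the minimum duration for SD (49 days from first dose, SAP 5.2.1) counts as disease control in DCR.
- Keep all treated as the main ORR denominator, with the existing response-evaluable analysis as supportive. Restricting the main denominator to measurable disease would depart from the protocol's own definition.
- Replace the case-by-case exclusion for lack of measurable disease in SAP 8.2.3 with a rule fixed before the data are reviewed.

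**Cost.** One eligibility clarification at the next amendment and a few SAP sentences. SAP version 1.0 incorporates changes only up to Revised Protocol 03, while the protocol stands at Revised Protocol 06, so a SAP update is due in any case. Depending on the option chosen, the price is a few bone-only candidates not enrolled or one additional small SAP rule.
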